8.3 Recording and reporting of SAEs AND SUSARs

8.3.1 Reporting requirements

All SAEs occurring from consent to 28 days post cessation of trial treatment must be recorded & reported by site (see table 2 for forms to be used and reporting timeline).

The investigator must immediately and not later than in 24 hours, report to the sponsor; all serious adverse events by emailing [contact] or by sending a fax to [contact].

For each SAEs / SUSARs the following information will be collected in a dedicated safety event reporting form (SERF):

CONFIDENTIAL

- full details in medical terms and case description
- event duration (start and end dates, if applicable)
- action taken
- outcome
- seriousness criteria
- causality (i.e. relatedness to trial drug / investigation), in the opinion of the investigator
- whether the event would be considered expected or unexpected.

Any change of condition or other follow-up information should be provided to the Sponsor as soon as it is available or at least within 24 hours of the information becoming available. Query responses should be also provided to the Sponsor within the requested timelines. Follow-up information and Query Response must be sent emailing [contact] or by sending a fax to [contact]. Events will be followed up until the event has been resolved or a final outcome has been reached.

All SAEs assigned by the PI or delegate (or following central review) as both suspected to be related to IMP-treatment and unexpected, will be classified as SUSARs and will be subject to expedited reporting to the Competent Authority. The Sponsor will inform CAs, ECs and ViiV of SUSARs within the required expedited reporting timescales.

Table 2: Safety Reporting Format & Timelines

Safety Data	Reporting Format	Timeline
All SAEs arising during the Clinical Trial, regardless of Investigator/designee causality assessments against IMP(s)	SERF	Site to report to sponsor within 24 hours of first becoming aware of the event.

CONFIDENTIAL

Pregnancy information for all female Clinical Trial Subjects who become pregnant while participating in the Clinical Trial and following exposure to an IMP.
	
SERF
	
Site to send to sponsor within 24 hours of first becoming aware of the pregnancy or the pregnancy outcome.

The subject will also be followed to determine the outcome of the pregnancy (including information on the status of the mother and child), which will also be reported to sponsor.
		

All liver events meeting the criteria for an SAE, including all events of possible drug-induced liver injury (DILI) with hyperbilirubinemia defined as ALT \geq 3X_{ULN} and bilirubin \geq 2X_{ULN} (>35% direct)
	
SERF
	
The SAE form must be completed and reported to the sponsor within 24 hours.

All Liver Chemistry Elevations that meet Liver Stopping Criteria (as defined in the Protocol), regardless of Investigator/designee causality assessments against IMP(s); and whether or not the event and/or associated signs and symptoms meet definitions of seriousness as outlined above
	
Liver Event CRF Modules i.e. VHL liver event CRF, liver imaging and/or liver biopsy CRFs
	
Site to complete the Liver event CRF modules and send to sponsor within one week of first becoming aware of the event

CONFIDENTIAL

Suicidality-related adverse events (PSRAEs) (as defined in the Protocol) that met the criteria for an SAE.	SERF PSRAE CRF Module	The SAE form must be completed and reported to the sponsor within 24 hours. The PSRAE CRF Module should be completed and reported to the sponsor within one week of the investigator diagnosing a possible suicidality-related adverse event
Deaths	Any AE, adverse reaction or unexpected adverse reaction that results in death should be reported as an SAE on an SERF	Site to report to sponsor within 24 hours of first becoming aware of the event.
Overdose	If the overdose fits the criteria of an SAE (see Section 8) it should be reported appropriately on an SERF	Site to report to sponsor within 24 hours of first becoming aware of the event.

All safety reports and reportable events listed on the above table (including Investigator causality) assessment should be reported in English to the sponsor.

Reporting Period

The SAEs, and pregnancy reports that are subject to the above reporting provisions are those that occur following the consent through to 28 days post cessation of trial treatment.

8.4 Responsibilities

Principal Investigator (PI):

Checking for AEs and ARs when participants attend for treatment / follow-up.

1. Using medical judgement in assigning seriousness, causality and expectedness using the Reference Safety Information approved for the trial.
2. Ensuring that all SAEs and SARs (including SUSARs) are recorded and reported to the Sponsor within 24 hours of becoming aware of the event and provide further follow-up information as soon as available. Ensuring that SAEs and SARs (including SUSARs) are chased with Sponsor

CONFIDENTIAL

if a record of receipt is not received.

3. Ensuring that AEs and ARs are recorded and reported to the Sponsor in line with the requirements of the protocol.

Chief Investigator (CI) / delegate or independent clinical reviewer:

1. Clinical oversight of the safety of patients participating in the trial, including an ongoing review of the risk / benefit.
2. Using medical judgement in assigning seriousness, causality and expectedness of SAEs where it has not been possible to obtain local medical assessment.
3. Using medical judgement in assigning expectedness
4. Immediate review of all SUSARs.
5. Review of specific SAEs and SARs in accordance with the trial risk assessment and protocol

Sponsor:

1. Central data collection and verification of AEs, ARs, SAEs, SARs and SUSARs according to the trial protocol.
2. Reporting safety information to the CI, delegate or independent clinical reviewer for the ongoing assessment of the risk / benefit.
3. Reporting safety information to the Data Safety Monitoring Board (DSMB) according to committee charter documents.
4. Expedited reporting of SUSARs to the Competent Authorities and ECs within required timelines in accordance with the applicable country legislations.
5. Notifying Investigators of SUSARs that occur within the trial.
6. Checking for and notifying PIs of updates to the Reference Safety Information for the trial.
7. See section 8.3.1 for details of reporting requirements to ViiV.

Data Safety Monitoring Board (DSMB):

In accordance with the DSMB Charter, periodically reviewing overall safety data to determine patterns and trends of events, or to identify safety issues, which would not be apparent on an individual case basis.

CONFIDENTIAL

8.5 Reporting urgent safety measures

It is the responsibility of the investigator to apply the appropriate level of Urgent Safety Measure (USM) for the safety and protection of each participant in this study in order to prevent harm. USMs may be applied without prior approval from the sponsor, Competent Authority (CA) or Ethics Committee but must be reported to the sponsor immediately who will then inform the CA and EC according to local regulation.

Please have full details including the action taken.

8.6 Development Safety Update Reports (DSUR)

The sponsor will be responsible for the production of DSURs once a year throughout the clinical trial, or on request, and their submission to relevant Competent Authorities and Ethics Committees as required within applicable timeframes.

9 STATISTICS AND DATA ANALYSIS

9.1 Sample size

This is a pilot proof of concept study to investigate whether complex regimens taken by patients with resistance mutations can be replaced by a simple two class single pill regimen safely in terms of viral load and adverse events.

No formal sample size calculation is performed. It is anticipated that data from 150 participants is adequate to meet the trial objectives (100 in the DTG/RPV arm and 50 in the control arm). The expected success rate is 95% based on the data reported by the SWORD 1 & 2 studies. If the observed success rate is 95% in the DTG/RPV arm at week 48 and varies from 95% to 100% in the control arm, with 150 participants (100 in the DTG/RPV arm and 50 in the control arm), the lower bound of the confidence interval of the difference in the success rate between the 2 arms (DTG/RPV – control) would varied from -9.3% to -7.4% (see table below).

Success rate		Difference	95% Confidence Interval	
DTG/RPV (n=100)	Control (n=50)		lower	upper
95%	95%	0.0%	-7.4%	7.4%
95%	96%	-1.0%	-7.9%	5.9%

CONFIDENTIAL

95%	97%	-2.0%	-8.4%	4.4%
95%	98%	-3.0%	-8.8%	2.8%
95%	99%	-4.0%	-9.1%	1.1%
95%	100%	-5.0%	-9.3%	-0.1%

In addition, we would like to show whether the observed success rate in the DTG/RPV arm is above 95%. Therefore, we estimated power for a one-sample proportion test (Binomial test) by varying the external threshold from 80% to 90% to detect the minimum effect size at which we will have 80% power to achieve the goal (see table below).

Ho (null hypothesis): $p = p_0$ versus Ha (alternative hypothesis): $p > p_0$

N	alpha	p	p0	delta	power
100	5%	95%	80%	15%	100%
100	5%	95%	81%	14%	99.9%
100	5%	95%	82%	13%	99.6%
100	5%	95%	83%	12%	98.9%
100	5%	95%	84%	11%	97.2%
100	5%	95%	85%	10%	93.7%
100	5%	95%	86%	9%	93.7%
100	5%	95%	87%	8%	87.2%
100	5%	95%	88%	7%	76.6%
100	5%	95%	89%	6%	61.6%
100	5%	95%	90%	5%	43.6%

We show that, with 100 individuals in the DTG/RPV arm, we will have a 95% probability to discard a combination for which efficacy is smaller than 87% and we will select with a power of 80% the strategy for which the efficacy is above or equal to 95%.

The power calculation was made using the statistical software package nQuery Advanced, using the exact test for single proportion module (Version 8.5.2.0).

9.2 Statistical analysis plan

The statistical analysis plan will be produced during the early stages of the clinical trial before the database has been locked for the first statistical analysis. This statistical analysis plan will describe the rules used for classification of the efficacy and safety data, the primary and secondary analyses and the format of the final tables, figures, and listings to be generated. The statistical analysis plan will be finalised and approved in line with applicable SOPs before any analysis is conducted.

CONFIDENTIAL

9.2.1 Summary of baseline data and flow of patients

The final analysis will be performed at the end of trial. A flow diagram will be produced, according to CONSORT standards, to show the disposition of all randomised patients up to the end of the trial.

Baseline data will be described according to the treatment arms: age, sex, ethnicity, length of prior ARV therapy and presence of NRTI and NNRTI mutations in historical resistance samples.

9.2.2 Primary outcome analysis

The primary endpoint will be a comparison of the percentage of participants with undetectable plasma HIV RNA levels at Week 48.

Undetectable will be defined as plasma RNA levels of <50 copies/ML. Participants with missing data at analysis time points will be considered as having lost undetectable plasma HIV-1 RNA levels. Any patient with HIV RNA levels >50 copies/ML at analysis time points will have a repeat test (see section 6.18 for repeat testing process). If the result from the repeat test is below 50 copies/ML, the patient will be classified as a responder. This is to prevent false positive HIV RNA results being classified as treatment failures.

The analysis will be performed using the FDA Snapshot method. The primary population for analysis will be Intent to Treat, including all randomised patients who have received at least one dose of study medication.

Participants will be categorised as follows, based on their HIV RNA results and disposition up to the end of the trial.

HIV RNA <50 copies/ML at Week 48

HIV RNA confirmed >50 copies/ML at Week 48 (virological failure)

Missing HIV RNA data – discontinued randomised treatment for adverse events

Missing HIV RNA data – discontinued randomised treatment for other reasons

The intention of this study is to be a comparative pilot study. All analysis details will be included in Statistical Analysis Plan.

CONFIDENTIAL

9.2.3 Secondary outcome analysis

Primary efficacy analysis repeated with (<200 copies/ml HIV RNA) at 24, 48, 96.

The primary efficacy analysis will be repeated for the Per Protocol population, excluding participants with serious protocol violations which could interfere with the reliability of the efficacy outcome. Examples would include taking other antiretroviral treatment within the first 48 weeks of treatment, incorrect randomisation or early discontinuation from the study for reasons unconnected to efficacy or safety. This analysis will be conducted to check the reliability of the results from the primary efficacy analysis.

In addition, a “Switch Included” analysis will be conducted, to check the outcomes of participants who discontinued randomised treatment for any reason. This analysis will follow the same methods as FDA Snapshot, but will include HIV RNA data from all participants with results available at Week 48, whether they are on or off randomised treatment. There will be no formal non inferiority outcome analysis as this is a pilot study.

All analysis details will be included in Statistical Analysis Plan.

9.3 Subgroup analyses

The sample size of 150 participants is too small to allow meaningful subgroup analyses. The two analyses described above (Per Protocol and Switch Included) will assess the reliability of the results from the primary efficacy analysis.

9.4 Adjusted analysis

The primary efficacy analysis will be by multiple logistic regression. This analysis will be adjusted for two baseline categorical variables which might influence the 48-week outcome: presence of M184V mutation at baseline and CD4 count at baseline (above versus below 350 cells/UI).

9.5 Interim analysis

An interim analysis will be performed when 120 participants reach the week 24 visit (corresponding to 80

CONFIDENTIAL

participants in the DTG/RPV arm and 40 participants in the control arm). This will include a primary efficacy analysis for the Per Protocol population, excluding participants with serious protocol violations which could interfere with the reliability of the efficacy outcome. This analysis will be conducted to check the reliability of the results from the primary efficacy analysis and will also include the number of patients that discontinued the study due to adverse event or death, and discontinued the study for other reasons.

In the ANRS 163 ETRAL trial (Katlama et al., JAC 2019), in which 10% of participants harboured viruses with K103N mutation, the proportion of participants in success at week 24 with a dual therapy with etravirine and raltegravir was estimated at 96.4% (95%CI 92.3 to 98.7). Therefore, for this interim analysis at week 24: The expected level of efficacy is 96%, and the unacceptable level of efficacy (p_0) is 87%. With $\alpha = 5\%$ (unilateral) and 80% power, if we include 80 participants in the DTG/RPV arm, we will consider that the treatment is effective to be continued if there are no more than 4 failures. We test the null hypothesis $H_0: p \leq 87\%$ versus the alternative hypothesis $H_a: p \geq 96\%$, with an 80% chance that the lower bound of the 95% confidence interval would exclude 87% if the true success rate (p) is 96%. This gives a 5% chance of continuing if $p = p_0$ and an 80% chance of continuing if $p \geq 96\%$.

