An interim analysis will be performed when 120 participants will reach the week 24 visit (corresponding to 80 participants in the DTG/RPV arm and 40 participants in the control arm). In the ANRS 163 ETRAL trial (Katlama et al., JAC 2019)(2), in which 10% of participants harboured viruses with K103N mutation, the proportion of participants in success at week 24 with a dual therapy with etravirine and raltegravir was estimated at 96.4% (95%CI 92.3 to 98.7). Therefore, for this interim analysis at week 24: The expected level of efficacy is 96%, and the unacceptable level of efficacy (p_0) is 87%. With $\alpha = 5\%$ (one-sided) and 80% power, if we include 80 participants in the DTG/RPV arm, we will consider that the treatment is effective to be continued if there are no more than 4 failures. We test the null hypothesis $H_0: p \leq 87\%$ versus the alternative hypothesis $H_a: p \geq 96\%$, with an 80% chance that the lower bound of the 95% confidence interval would exclude 87% if the true success rate (p) is 96%. This gives a 5% chance of continuing if $p = p_0$ and an 80% chance of continuing if $p \geq 96$.

6. General Considerations

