6.6 Interim analysis

One administrative statistical interim analysis is planned on the primary efficacy endpoint to show whether the efficacy of the dual therapy with DTG and RPV is above 96% after week 24. This interim analysis is planned to take place when 120 participants (80 in the DTG/RPV arm and 40 in the control) have reached the 24-week visit. It will be done following week 24 with the mITT population. The 95% two-sided confidence interval of the percentage of patients in therapeutic success will be calculated and DTG/RPV will be considered as an acceptable strategy if the lower bound is greater than 87%. The strategy will be considered unacceptable if there are 18 therapeutic failures or more. With 18 failures among 80 subjects in the DTG/RPV arm, the observed proportion of success is 77.5% and the associated CI is 66.7% to 86.1%, so just excluding 87%. Additional issues could include treatment

emergent drug resistance, serious adverse events or high rates of discontinuation for adverse events. The interim analysis will also explore whether the lower limit of the 95% confidence interval of the difference in the percentage of participants with therapeutic success between the DTG/RPV arm and the control arm (DTG/RPV- control) remain in acceptable range (above -13%).

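### Protocol and SAP name different populations for the week-24 interim, and neither ties the 4-failure rule to one, so the same data can meet it on one set and miss it on the other

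*Protocol*

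**What the plan says.** **Population.** Protocol 9.5 describes the interim efficacy work in one statement: "This will include a primary efficacy analysis for the Per Protocol population". It gives the purpose as checking the reliability of the primary efficacy analysis, and names no other population. SAP 6.6 says of the same interim: "It will be done following week 24 with the mITT population". Protocol 9.7 makes ITT-exposed the primary population, and SAP 6.3.1 uses its equivalent, mITT.

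**Rule.** Protocol 9.5 and SAP section 5 carry the same sentence: "we will consider that the treatment is effective to be continued if there are no more than 4 failures". It is framed on 80 participants in the DTG/RPV arm, with 87% as the unacceptable and 96% as the expected success rate. It names no population. SAP 6.6 restates acceptance as a two-sided 95% lower bound above 87%. It calls the strategy unacceptable at 18 or more therapeutic failures.

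**Who is in each set.** Protocol 9.7 and SAP 6.3.2 remove from per-protocol those who leave early for reasons unrelated to efficacy or safety. SAP 7.2 adds withdrawn consent, loss to follow-up and a missing primary-endpoint value as serious deviations. On mITT, SAP 3.2.1 counts discontinuation as therapeutic failure, and SAP 6.5 counts missing data as loss of suppression.

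**The concern.** The two sets treat the same people in opposite ways. A participant who moves away at week 10 while suppressed is one failure among 80 on mITT and is absent from per-protocol. A cut of 4 leaves little room, so one or two such people can decide whether it is met.

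A DSMB statistician working from Protocol 9.5 finds only the per-protocol set, followed by a rule with no population. One working from SAP 6.6 finds only mITT. The difference has a direction: removing unrelated dropouts can only lower the failure count, so a literal reading of Protocol 9.5 tilts the check toward a pass. The error rates were also worked out for 80 participants, and per-protocol will usually have fewer.

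**Working it through.** **Inputs.** n = 80, cut of 4 failures, 87% and 96% (Protocol 9.5, SAP section 5); lower bound above 87% and 18 failures (SAP 6.6). Protocol 6.12 expects 15% loss to follow-up but gives no time point, so the dropout rates by week 24 used below are assumptions.

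**1. The plan's own figures.** With failure probability q, P(X ≤ 4) = Σ(k = 0 to 4) C(80,k) q^k (1−q)^(80−k).
- q = 0.04: 78.4%, close to the stated 80%.
- q = 0.13: 1.66%. The plan says "This gives a 5% chance of continuing if" true success equals 87%, so this figure does not reproduce. A cut of 5 would give 4.26% (and 89.9% at q = 0.04). This gap is present on the full 80 and does not come from the choice of population.

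**2. Count rule and interval rule.** The exact (Clopper–Pearson) lower limit for x successes of n is the 2.5% quantile of Beta(x, n−x+1).
- 76/80: 87.7%, met.
- 75/80: 86.0%, missed.

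At n = 80 the two forms are therefore the same rule. The SAP does not name the interval method here, but its interval for 18 failures of 80 (66.7% to 86.1%) agrees with the exact one (66.8% to 86.1%). The choice matters: a Wald interval for 75/80 is 93.75% ± 1.96 × √(0.9375 × 0.0625/80) = 93.75% ± 5.30%. Its lower limit is 88.4%, which would pass.

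**3. Same data, two populations.** In each row, all failures beyond four are unrelated dropouts.

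| mITT failures | mITT lower limit | Per-protocol failures | Per-protocol lower limit |
|---|---|---|---|
| 5/80 | 86.0% missed | 4/79 | 87.5% met |
| 6/80 | 84.4% missed | 4/78 | 87.4% met |
| 7/80 | 82.8% missed | 4/77 | 87.2% met |
| 8/80 | 81.2% missed | 4/76 | 87.1% met |

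At n = 75, 4 failures give 86.90%. Below 76 participants the count rule and the interval rule part company.

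**4. Probabilities.** Let v be virological failure and d unrelated dropout, as shares of the 80. The mITT failure count is Bin(80, v+d). Per-protocol failures are Bin(80, v). For the interval rule, dropouts D ~ Bin(80, d) and failures given D ~ Bin(80−D, v/(1−d)) were enumerated.

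| v, d (assumed) | mITT success | Rule met, mITT | Rule met, PP by count | Rule met, PP by lower limit |
|---|---|---|---|---|
| 2%, 3% | 95% | 63% | 98% | 97% |
| 3%, 5% | 92% | 22% | 91% | 86% |
| 5%, 8% | 87% | 1.7% | 63% | 47% |

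Light dropout is enough to matter. With 1% unrelated dropout and 96% success among those who stay, the figures are 63.5% on mITT and 78.9% per-protocol under either form.

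**5. How far apart the outcomes can be.** For per-protocol to meet the count while mITT reaches 18 failures, at least 18 − 4 = 14 of 80 must be excluded. In the three scenarios of step 4 the probability is 0.13% for the last and below 0.001% for the other two.

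**The case against.** The best defence is that the documents can be read together. Protocol 9.5 presents the per-protocol analysis as something the interim will include, as a reliability check, which implies a separate primary analysis. The rule stands apart from it and is framed on 80 included participants. Protocol 9.7 makes ITT-exposed primary, Protocol 9.2.2 sends details to the SAP, and the SAP says mITT. On that reading the rule already runs on mITT. This reading is reasonable, and it rules out the inference that the protocol orders the rule to be run per-protocol. It does not clear the text: Protocol 9.5 never specifies the primary interim analysis that the per-protocol one is meant to check.

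Three further inferences are tempting and are not supported.

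- *Opposite decisions, continue against stop.* SAP 6.6 leaves 5 to 17 failures of 80 neither acceptable nor unacceptable, and calls the interim administrative. Protocol 9.6 bases stopping on efficacy and safety together.
- *The only efficacy safeguard before week 48.* SAP 6.6 also has the 18-failure boundary and a between-arm check at −13%. Protocol 9.6 lets the DSMB meet at other times, and the risk table in Protocol 1.1 allows a review triggered by virological withdrawals.
- *Early stoppers fall outside the interim.* The trigger is worded "An interim analysis will be performed when 120 participants reach the week 24 visit", which could suggest this. It sets timing. SAP 3.2.1 and 6.5 count discontinuation and missing data as failure, and SAP 8.1 divides by the whole mITT set.

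**Conclusion.** The point holds as an unresolved conflict over the interim population. One unrelated dropout among five failures is enough for the criterion to be met on per-protocol and missed on mITT, and that example needs no assumed rate. The probabilities do rest on assumed splits between virological failure and unrelated dropout. Over the splits tried, the chance of meeting the rule rises from 63% to 97–98% at the mild end, and from 1.7% to 47–63% where true mITT success sits at the unacceptable 87%. The lower figure of each pair uses the exact lower limit and the higher uses the fixed count.

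The error is one-sided, toward meeting the criterion. What changes is the efficacy signal given to the DSMB; the count alone does not decide whether the trial goes on. The mismatch between the stated 5% and the exact 1.66% is separate, and naming the population will not remove it.

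**What to change.** Reconcile Protocol 9.5 with SAP section 5 and SAP 6.6 so that all three say:

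- The interim efficacy criterion is evaluated on DTG/RPV participants in the mITT (ITT-exposed) population, with those who discontinued before week 24 counted as failures.
- The per-protocol analysis is supportive only.
- The criterion is the exact (Clopper–Pearson) two-sided 95% lower limit against 87%. This equals at most 4 failures at n = 80 and still works if the arm has a different number at the data cut.

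This follows the sponsor's own choice of primary population. The cost is a sentence or so in each document, with no new data. It does not settle what 5 to 17 failures should mean, which stays with the DSMB's combined review under Protocol 9.6.

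### The week-24 interim rule (continue with at most 4 failures of 80) has a 1.7% chance of continuing at 87% efficacy, not the stated 5%; the alpha label does not match the cut

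*Protocol*

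**What the plan says.** Protocol 9.5 plans one interim look once 120 participants have reached week 24, 80 of them on DTG/RPV. It takes 96% as the expected success rate and 87% as the unacceptable one. Alpha is 5% ("unilateral) and 80% power, if we include 80 participants in the DTG/RPV arm"), and the rule is that "we will consider that the treatment is effective to be continued if there are no more than 4 failures". The paragraph asks for an 80% chance that the lower 95% confidence bound excludes 87% when the true rate is 96%. It then gives the rule's error rate: "This gives a 5% chance of continuing if" the true rate is 87%, paired with an 80% chance of continuing at 96%.

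SAP section 5 repeats this text, with alpha described as "one-sided) and 80% power, if we include 80 participants in the DTG/RPV arm".

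SAP 6.6 states the criterion through a two-sided 95% interval for the success rate: "DTG/RPV will be considered as an acceptable strategy if the lower bound is greater than 87" (per cent). At the other end, "The strategy will be considered unacceptable if there are 18 therapeutic failures or more", explained by the remark that "the associated CI is 66.7% to 86.1%, so just excluding 87" (per cent).

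Protocol 9.1 and SAP section 5 also give a power table for 100 participants, with alpha 5%, computed with an exact single-proportion test.

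**The concern.** The paragraph gives every input needed to compute the chance of continuing at 87%, and the printed 5% does not follow from them. The rule is far stricter than a one-sided 5% test. The apparent cause is that alpha is labelled one-sided 5%, while the cut was set by a two-sided 95% interval, whose lower limit is a one-sided 2.5% bound.

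At stake is an accurate statement of how the interim rule behaves. A DSMB member or reader who relies on the sentence would believe the risk of continuing with an unacceptable regimen is three times what it is (5 / 1.7 ≈ 3). A statistician who tries to rebuild the cut from the declared alpha would arrive at 5 failures, not 4.

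**Working it through.** **Inputs.** n = 80 in the DTG/RPV arm; unacceptable success 87% (failure 13%); expected success 96% (failure 4%); continue if failures X ≤ 4; declared alpha 5% one-sided (Protocol 9.5, SAP 5). Two-sided 95% interval, lower bound above 87% (SAP 6.6).

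**1. The printed error rate.** P(continue) = Σ C(80,k) qᵏ (1−q)⁸⁰⁻ᵏ for k = 0 to 4, where q is the failure probability.

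- At q = 0.13: 0.00001 + 0.00017 + 0.00102 + 0.00398 + 0.01144 = 0.0166, or **1.7%** (printed: 5%).
- At q = 0.04: 0.0382 + 0.1272 + 0.2094 + 0.2268 + 0.1820 = 0.784, or **78.4%** (printed: 80%; close, and not disputed).

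Approximations do not recover 5% either: normal 1.67%, normal with continuity correction 2.49%, Poisson 2.25%.

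**2. Where the cut of 4 comes from.** Exact (Clopper-Pearson) lower bounds for the success rate:

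| Failures of 80 | Two-sided 95% lower bound | One-sided 95% lower bound | P(X ≤ this) at 87% | P(X ≤ this) at 96% |
|---|---|---|---|---|
| 4 | 87.7% | 88.9% | 1.7% | 78.4% |
| 5 | 86.0% | 87.3% | 4.3% | 89.9% |
| 6 | 84.4% | 85.7% | 9.1% | 95.9% |

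The two-sided 95% bound exceeds 87% at 4 failures and not at 5, so the SAP 6.6 criterion gives a cut of 4. That is a one-sided 2.5% test, with attained size 1.7%. The declared one-sided 5% would give a cut of 5, with attained size 4.3%.

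**3. Which interval SAP 6.6 uses.** It names no method, but its worked example points to the exact one. For 18 failures of 80 the exact two-sided 95% interval is 66.8% to 86.1%; the SAP prints 66.7% to 86.1%. The simple normal interval would be 0.775 ± 1.96 × √(0.775 × 0.225 / 80) = 0.775 ± 0.0915, or 68.3% to 86.7%, which does not match.

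**4. Convention in the n = 100 table.** At a threshold of 87%:

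- Exact one-sided 5% requires at least 93 successes (size 4.3%), with power 87.2% at 95%. This reproduces the printed 87.2%.
- One-sided 2.5% requires at least 94 (size 1.9%), with power 76.6%.

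So in the sample-size table alpha 5% is a one-sided 5% test, while the interim cut under the same label behaves as one-sided 2.5%.

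**The case against.** **The 5% is a nominal ceiling.** A rule with true size 1.7% respects a 5% limit, and a ceiling does not oblige the sponsor to use the largest cut that fits under it. That is fair as far as it goes. The sentence, however, is worded as what the rule delivers, not as an upper limit. Discreteness does not explain the gap either: it accounts for 4.3% in place of 5%, not for 1.7%.

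**The error is harmless.** The true risk of continuing at 87% is lower than printed. SAP 6.6 calls the look administrative, the trial is a pilot with no formal sample-size calculation, and correcting the figure changes neither the rule nor the week-48 analysis. All of this stands and limits the weight of the point.

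**Stronger readings that a reader might infer, and that the documents do not support:**

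- *The decision at exactly 5 failures is ambiguous.* It is not. Protocol 9.5 and SAP 5 both say at most 4, and the SAP 6.6 interval also fails at 5 failures (86.0%). No document contains a rule of at most 5.
- *Results of 5 to 17 failures have no handling.* The two interval statements in SAP 6.6 imply a middle zone in which the interval contains 87%. Protocol 9.6 bases stopping on a combined DSMB evaluation of efficacy and safety. What is missing is a cross-reference.
- *The two documents use conflicting interim populations.* Protocol 9.5 mentions a Per Protocol analysis, but as a check on reliability. Protocol 9.7 makes the exposed intent-to-treat population primary, and SAP 6.6 names mITT for the interim. Only a label is missing.

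**Conclusion.** The point holds as an error in a stated operating characteristic. The rule of at most 4 failures of 80 has a 1.7% chance of continuing at 87% success, not 5%; its power of 78.4% at 96% agrees with the printed 80% to within 2 points. The alpha label (one-sided 5%) and the cut (one-sided 2.5%, from the two-sided 95% interval) belong to different conventions.

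The error is conservative and does not alter what the interim would decide. It should be fixed because the printed rate is wrong in both documents and the correction costs almost nothing.

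Assumptions: exactly 80 evaluable DTG/RPV participants, independent outcomes, and an exact interval in SAP 6.6. The first is the documents' own figure. The last is inferred from the 18-failure example, as is the origin of the cut of 4, which the documents do not state.

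**What to change.** In Protocol 9.5 and SAP section 5:

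1. Describe the interim criterion as the lower limit of the exact two-sided 95% interval exceeding 87% (one-sided 2.5%).
2. Replace the printed 5% and 80% with about 1.7% at 87% and about 78% at 96% for at most 4 failures of 80.

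If the sponsor prefers to keep the one-sided 5% label, the label, the cut and the SAP 6.6 interval must be reconciled with one another. For reference, the exact one-sided 5% cut is at most 5 of 80, with 4.3% and 89.9%. The choice is the sponsor's; the need is for one convention with its own figures.

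Optional wording: in SAP 6.6, refer results of 5 to 17 failures to the combined DSMB evaluation in Protocol 9.6; in Protocol 9.5, label the Per Protocol analysis as the sensitivity analysis to the mITT interim.

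The cost is a few sentences and restated figures, with no extra participants, no new data and no change to the week-48 analysis.
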